4. WBC <3,000
5. Serious Infections that require hospitalization.

The investigators will also review the data every 6 months to ensure there are no safety concerns or clear inferiority in one arm that would warrant early termination of the trial.

C. Outcomes monitoring

The following outcomes will be collected throughout the study period as appropriate:

1. Disease flare defined as a BVAS/WG ≥ 2 (**primary aim**). A subgroup analysis will be performed by ANCA subtype.
2. Proportion of patients with serious adverse events (SAEs), including all episodes of LON.
3. Number of infections (mild and severe).
4. Total rituximab utilization during the study period.

5. Patient quality of life assessment using the SF-36v2 and EQ-5D-5L surveys every 6 months
6. Number of major (modified BVAS-WG ≥ 3) relapses
7. Survival
8. Hypogammaglobulinemia (IgG < 400 mg/dL)

D. Adverse event reporting guidelines

All adverse events will be reported per PHRC guidelines which includes unanticipated problems involving risks to subjects/others, including adverse events, within 5 working days/7 calendar days of the date that the investigator first became aware of the problem.

References

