Data from randomized clinical trials and observational studies suggest relapse is common if rituximab is discontinued indefinitely. Among patients in the RAVE trial who achieved complete remission following treatment with rituximab, 32% had a relapse within 18 months(9).

Furthermore, Alberici *et al* reported that 41% of patients who received maintenance rituximab every 6 months for 24 months relapsed at a median of 34.4 months following discontinuation of therapy(17). Predictors of relapse included return of B cells and change from ANCA negativity to positivity(17).

Survival of ANCA vasculitis patients undergoing rituximab-induced continuous B cell depletion

A prospective and longitudinal clinical trial is needed to determine the ideal treatment strategy for long-term maintenance of remission. Here we propose to compare 2 strategies once patients have

been in sustained remission on scheduled rituximab dosing with a goal of undetectable B cells for greater than or equal to 2 years. Target enrollment is 200 subjects over 48 months from the time the first patient is enrolled to be followed for a common close out date of 36 months after the last subject is enrolled.

The study design is an open-label, single center, randomized and two-arm controlled trial to evaluate the optimal maintenance of remission strategy that provides the best relapse-free survival in patients with ANCA vasculitis as determined by relapse-free remission at 18, 24 and 36 months from enrollment. Subjects with ANCA vasculitis in sustained remission on regularly scheduled rituximab infusions with a goal of undetectable B cells for a minimum of two years who meet specific entry criteria will be randomized with stratification based on ANCA subtype and rituximab vintage (i.e., duration of continuous rituximab prior to enrollment) to one of two arms :

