- 1. Primary Aim: To determine whether a rituximab-dosing protocol based on: 1) reconstitution of peripheral B cells or 2) a serologic ANCA flare is more efficacious in preventing relapse in patients with ANCA vasculitis.** Eligible patients will have completed a minimum of 2 years of rituximab maintenance therapy without relapse. The endpoint will be disease relapse defined as a BVAS/WG ≥ 2 . Analysis will also be stratified based on ANCA subtype (due to differences in relapse between patients with MPO and PR3 ANCA) and rituximab vintage.
- 2. Secondary Aim 1: To determine whether a rituximab-dosing protocol based on: 1) reconstitution of peripheral B cells or 2) a serologic ANCA flare is associated with more serious adverse events.** Serious adverse events of interest include those related to vasculitis activity and those that develop as a consequence of rituximab therapy. The main rituximab-associated serious adverse events noted in our cohort are infection, late-onset of neutropenia, and infusion reactions(10)
- 3. Secondary Aim 2: To determine whether a rituximab-dosing protocol based on: 1) reconstitution or peripheral B cells or 2) a serologic ANCA flare is associated with a greater composite of disease relapse (BVAS/WG ≥ 2) and serious adverse events.**
- 4. Secondary Aim 3: To determine whether a rituximab-dosing protocol based on: 1) reconstitution of peripheral B cells or 2) a serologic ANCA flare is associated with greater rituximab utilization during the study period.** While effective, rituximab therapy is costly and increases health care expenditures. Evaluation of the relative cost of the 2 dosing-strategies will assist in the application of these dosing-strategies to the broad population of patients with ANCA vasculitis.

III. Subject Selection

Patients with ANCA vasculitis who are seen at MGH will be recruited as subjects and inclusion and exclusion criteria are detailed below.

A. Inclusion and exclusion criteria

Inclusion criteria:

1. All patients must be able and willing to give written informed consent and comply with the requirements of the study protocol.

2. Diagnosis: ANCA vasculitis as defined by a positive MPO- and/or PR3-ANCA test together with clinical features characteristic of ANCA-positive diseases as detailed in the 2012 Chapel Hill Consensus Conference Definitions(18).
3. eGFR \geq 20 cc/min/1.73m²
4. Age: 18-82 years old

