Rituximab (Rituxan, Genentech), which is FDA-approved for GPA and MPA, will be used in the study.

C. Devices to be used

Not applicable

D. Procedures/surgical interventions

Not applicable

E. Data to be collected and when the data is to be collected

At present, there is no standard of care for maintenance of remission in ANCA vasculitis beyond the two-year mark; thus, the role of continuous versus intermittent B cell depletion requires investigation. Efficacy and toxicity are the foci of our outcome analysis for this study and will be assessed through analysis of primary and secondary endpoints.

The following variables will be collected at EACH study visit:

1. VDI (every 6 months)
2. Modified BVAS/WG
3. Laboratory data at baseline and at subsequent visits
 - a. Complete Blood Count
 - b. Comprehensive Metabolic Panel
 - c. eGFR
 - d. ANCA titer
 - e. ESR
 - f. CRP

- g. Immunoglobulin levels (every 6 months)
 - h. Urinalysis
 - i. Urine Hcg for women of child bearing potential (only at screening and when reinfused with rituximab)
 - j. Flow cytometric analysis of peripheral B and T lymphocyte markers
4. Concomitant medications at each visit
 5. Adverse events assessment

VI. Biostatistical Analysis

A. Specific data variables being collected for the study (e.g. data collection sheets)

Data variables collected are listed above and we will also verify contact information at each visit to ensure appropriate follow-up.

B. Study endpoints

Primary endpoints:

1. Disease flare defined as a BVAS/WG ≥ 2 . A subgroup analysis will be performed by ANCA subtype.

Secondary endpoints:

1. Proportion of patients with serious adverse events (SAEs), including all episodes of Late Onset Neutropenia (LON, absolute neutrophil count < 1000 cells/mm³)
2. The composite of disease flare (defined as BVAS/WG ≥ 2) and serious adverse events.
3. Total rituximab utilization during the study period
4. Accrued organ damage as assessed by the Vasculitis Damage Index (VDI)
5. Patient quality of life assessment using the SF-36v2 and EQ-5D-5L surveys every 6 months
6. Number of major (modified BVAS-WG ≥ 3) relapses
7. Survival
8. Hypogammaglobulinemia (IgG < 400 mg/dL)
9. All infections

C. Statistical methods

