Data will be analyzed by the intention-to-treat principle. Randomization will be stratified on ANCA subtype (MPO vs PR3) and rituximab vintage (< 3 years vs > 3 years). Rituximab vintage is the duration of continuous rituximab therapy administered prior to enrollment in the study. We have contracted with the company StudyTRAX to perform randomization on stratified variables via random permuted blocks.

Continuous data will be summarized using descriptive statistics. Continuous data will be assessed using the t-test or Wilcoxon rank-sum test as appropriate. Categorical data will be assessed using the Chi-square and the Fisher exact tests as appropriate. The probability of remaining free of relapse will be estimated using the Kaplan-Meier method. The difference between the two

treatment strategies will be assessed using the log-rank test. *P* values of 0.05 will be considered significant.

D. Power analysis

Using a two-sided logrank test with an alpha level of 0.05, a projected relapse risk of 15% in the superior group and 30% in the inferior group, and an estimated enrollment time of 36 months, it was determined that 180 patients are required to detect a significant difference with a power of 0.80. We aim to enroll 200 patients in the study.

VII. Risks and Discomforts

Subjects may experience side effects while receiving rituximab, which is given as part of their regular medical care for their GPA or MPA. As per the entry criteria, subjects have been on rituximab for 2 years prior to enrollment, the side effects have been discussed in detail and a signed consent for rituximab is obtained for every patient receiving rituximab at the first dose and annually thereafter.

The effects of rituximab on a fetus are unknown and may be harmful. Individuals of childbearing potential should use effective birth control during treatment and for 12 months after their last rituximab infusion. Prior to any infusion of rituximab to a woman of childbearing potential, a urine pregnancy test is performed and recorded. If a woman is found to be pregnant, she will then be removed from the study and followed based on best medical judgment as deemed appropriate by the clinician investigator.

A. Complications of surgical and non-surgical procedures

Not applicable

B. Drug side effects and toxicities

Common side effects of Rituxan

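### The six-monthly reviews can end the trial for clear inferiority of one arm with no criterion and no reporting rule, so the two-sided 5% level is not assured

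*Combined protocol and SAP*

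**What the plan says.** Section IX.B (Safety monitoring) ends with an instruction that the investigators "review the data every 6 months to ensure there are no safety concerns or clear inferiority in one arm that would warrant early termination". It gives two grounds, joined by an or: safety concerns, and clear inferiority of one arm. It names no endpoint, test, threshold or minimum number of relapses. It does not say what may be concluded from a trial that stops on the second ground.

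Section IX.C follows directly. It lists outcomes to be collected, with disease flare first and marked as the primary aim, but ties none of them to the six-monthly review.

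Section VI.C says that the difference between the two "treatment strategies will be assessed using the log-rank test" and that P "values of 0.05 will be considered significant". Section VI.D sizes the trial "Using a two-sided logrank test with an alpha level of 0.05". Neither section mentions interim looks or an adjustment for them. The design paragraph in section I states: "The study design is an open-label, single center, randomized and two-arm controlled trial".

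**The concern.** Both arms are active dosing strategies and the test is two-sided. If inferiority is judged on relapse, finding one arm clearly inferior is the same as finding the other superior. Such a stop could therefore be read as a primary efficacy result, unlike a futility stop, which cannot add false-positive claims.

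The people applying the criterion are the investigators of an open-label trial. With nothing written down, the bar would be set by people who have already seen results by arm, and it cannot be soundly supplied afterwards. After an early stop, readers could not tell whether the bar had been strict or lenient, or whether the ground was safety or efficacy. An early stop is a realistic outcome: under the planned effect, even a p<0.001 rule stops 28-45% of simulated trials early, depending on follow-up and dropout.

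**Working it through.** **1. The plan's own figure.** Inputs from VI.D: 15% vs 30% relapse, two-sided 0.05, power 0.80, 36 months' enrolment. Assumed: the risks are 36-month risks, relapse is exponential, accrual is uniform, and there is no dropout. Follow-up to 36 months after the last enrolment is from section I.

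- Hazard ratio = ln(0.85)/ln(0.70) = 0.456; its inverse is 2.19.
- Freedman events = (1.96 + 0.84)² × [(1 + 0.456)/(1 − 0.456)]², which rounds up to 57.
- Event probability over 36 + 36 months: 1 − (0.85 − 0.7225)/0.1625 = 0.215 and 1 − (0.70 − 0.49)/0.3567 = 0.411; mean 0.313.
- N = 57/0.313 = 182, against 180 stated.

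The stated size is thus reproduced, within 3%, by a single-look design with nothing set aside for interim looks.

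**2. Number of looks.** Enrolment takes 36 months in IV.B and VI.D, but section I says "Target enrollment is 200 subjects over 48 months from the time the first patient is enrolled". Adding 36 months gives 72 or 84 months. At one look every 6 months that is 72/6 = 12 or 84/6 = 14, including the final one.

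**3. Overall type I error.** I simulated log-rank tests at each look with no true difference: 200 patients, 1:1, 22.5% relapse at 36 months in both arms (the midpoint of 15% and 30%). Follow-up ran either to the common close-out or to visit 16. Visit 16 falls at 6 + 14 × 3 = 48 months from Day 0, which is 42 months after enrolment. Scenarios with no dropout and with 5% a year were run. The lower end of each range in the middle column generally comes from requiring 20 relapses before the first look, and the upper end from testing at every look.

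| Level at which reviewers act (final test at 0.05) | Early stop reported as a difference | Early stop carries no claim |
|---|---|---|
| p<0.001 | about 5% (at most about 0.3 points above a single final test) | about 5% |
| p<0.01 | 6-8% | 3-4% |
| p<0.05 | 12-23% | under 1% |

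With 15% or 30% relapse in both arms instead, the middle column is 4.8-5.2%, 5-8% and 10-23%.

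**4. Power under 15% vs 30%.** Single final test against the p<0.001 rule, for 36/48 months' accrual:

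- to close-out: 85.9/88.8% against 85.9/88.9%;
- to visit 16: 78.6/78.3% against 78.7/78.4%;
- to visit 16 with 5% yearly dropout: 74.4/73.7% against 74.4/73.8%.

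**5. What p<0.001 means in relapses.** With equal arms, Z = (d1 − d2)/√(d1 + d2), and p<0.001 needs Z above 3.29.

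- 18 vs 2: 16/√20 = 3.58, crosses.
- 25 vs 5: 20/√30 = 3.65, crosses.
- 31 vs 9: 22/√40 = 3.48, crosses.
- 15 vs 5: 10/√20 = 2.24, p about 0.025, does not cross.

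**6. Safety stops driven by severe relapses.** VI.B lists as a secondary endpoint "Number of major (modified BVAS-WG ≥ 3) relapses". Assume that 30% or 50% of relapses are major, that stopping is possible from 5 major relapses, and that follow-up runs to close-out. If such a stop were reported as showing one arm inferior, overall error is 6.8-7.7% (stopping at p<0.01) or 16-20% (p<0.05). If it is reported as a safety stop unless relapse also reaches p<0.001, error is 4.4-4.6% or 2.8-3.8%. Power for the efficacy claim then falls to 66-77% or 35-56%.

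**The case against.** The clause sits under safety monitoring, straight after a list of patient withdrawals that includes BVAS-WG of 2 or more, and section VII.C treats relapse as a harm. Nothing says that a stop for inferiority would be announced as a significant primary result. The word clear also suggests a high bar. If the bar is high, or if a stop carries no claim, the 5% level is safe and may even be conservative.

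Most of this stands. A reader might infer from the 12-23% row that the trial's error rate is inflated several-fold. The documents do not support that: it needs both a p<0.05 trigger and an early stop reported as a difference, and the plan states neither. Nor is IX.C silent on relapse, since flare heads its list.

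What does not stand is that the gap is harmless. The sentence separates inferiority from safety, IX.C does not link flare to the decision, and no text commits the investigators to a strict bar or to making no claim. The choice of boundary on an endpoint that is also a harm is a fair matter for the sponsor and the ethics committee. The essential request is a stated criterion and a stated reporting rule.

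**Conclusion.** The point holds as a gap in specification. Depending on two things the plan leaves open, the bar used at the reviews and how an early stop is reported, overall two-sided error could lie anywhere from under 1% to about 23%. With a strict bar it stays at about 5% under either reporting choice. These figures rest on assumed exponential relapse, uniform accrual, 1:1 allocation and a log-rank test of flare at each review. Varying the relapse rate, accrual period, follow-up cap and dropout does not change the conclusion. The purely safety part of the review need not affect the error rate. This should be corrected because the remedy is cheap and has to be in place before results by arm inform a decision; it is not evidence that the trial's error rate is wrong.

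**What to change.** State in IX.B and VI.C:

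1. An early stop is reported as showing one arm inferior on relapse (BVAS/WG of 2 or more) only if the primary log-rank test reaches two-sided p<0.001 at that review. The final test stays at 0.05. An alpha-spending boundary is an acceptable alternative; an O'Brien-Fleming type with equally spaced information would put the final p at about 0.036 (12 looks) or 0.035 (14 looks).
2. The six-monthly safety review, and stopping for safety at the reviewers' judgement, including because of relapses, are unchanged.
3. An early stop that does not meet the boundary is reported as a safety stop, not as a positive primary result.

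This takes a few sentences, with no added patients or staff and no power loss from the p<0.001 boundary itself. Four downsides should be accepted openly:

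- A stop at the boundary overstates the effect: the median Cox hazard ratio is about 3.1-3.5 when the true value is 2.2.
- A moderate early difference, such as 15 vs 5 relapses, does not support an inferiority claim.
- If safety stops on major relapses occur, power for the efficacy claim falls to the levels in step 6.
- The investigators still see results by arm; the rule limits what they may claim, not what they see.
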